Primary Objectives:

The primary objectives of this study are:

1. To evaluate the efficacy of repeated dosing with CTAP101 ER Capsules versus placebo in reducing plasma intact parathyroid hormone (iPTH) by $\geq 30\%$ from pre-treatment baseline;
2. To investigate the safety and tolerability of repeated dosing with CTAP101 Capsules; and,
3. To assess the pharmacokinetic (PK) profile of 25-hydroxyvitamin D₃ after repeated doses of CTAP101 Capsules in pediatric subjects of ages 8 to <18 years with secondary hyperparathyroidism (SHPT), stage 3 or 4 chronic kidney disease (CKD) and vitamin D insufficiency (VDI).

Secondary Objectives:

The secondary objectives of this study are:

1. To evaluate the efficacy of repeated dosing with CTAP101 Capsules versus placebo in raising serum total 25-hydroxyvitamin D to ≥ 30 ng/mL;
2. To determine the time courses of mean absolute changes from pre-treatment baseline in serum total 25-hydroxyvitamin D and plasma iPTH during administration of repeated doses of CTAP101 Capsules;

3. To assess the pharmacodynamic (PD) effects of repeated doses of CTAP101 Capsules versus placebo on mean serum calcium (corrected for albumin), serum phosphorus and serum calcium-times-phosphorus (CaxP) product, and the change in mean urine calcium:creatinine ratio; and,
4. To evaluate the safety of CTAP101 Capsules versus placebo with regard to the incidence of hypercalcemia and hyperphosphatemia.

Study Design:

This is a phase 3, multi-center, randomized, double-blind, placebo-controlled study which will be conducted primarily or entirely within the United States (US). The study will involve approximately 108 eligible subjects, balanced for gender and CKD stage, having ages of 8 to <18 years, SHPT, stage 3 or 4 CKD and VDI. Approximately 72 subjects having ages of 12 to <18 years will be enrolled initially (Cohort 1) and, after prior approval from the US Food and Drug Administration (FDA), another approximately 36 subjects having ages of 8 to <12 years will be enrolled (Cohort 2). Subjects in both cohorts will be randomized in a 2:1 ratio into two treatment groups to receive a daily bedtime dosage of (a) CTAP101 Capsules, or (b) matching placebo for 26-weeks. Subjects in Cohort 1 who are assigned to treatment with CTAP101 Capsules will start dosing at 30 mcg/day (1 CTAP101 Capsule) and, at the end of 12-weeks of treatment, will undergo upward dose titration to 60 mcg per day (two CTAP101 Capsules) provided that (a) plasma iPTH has not decreased by at least 30% from pretreatment baseline, (b) serum calcium (corrected for albumin) is <9.8 mg/dL, (c) serum phosphorus is ≤ 5.5 mg/dL and (d) serum total 25-hydroxyvitamin D is ≤ 65 ng/mL. The initial dosage in Cohort 2 will be determined based on an interim analysis of data obtained from Cohort 1, as described below. The efficacy of CTAP101 Capsules (compared to placebo) in treating SHPT will be assessed from multiple plasma iPTH and serum 25-hydroxyvitamin D levels obtained in the efficacy assessment period (EAP), defined as the last 6 weeks of the 26-week treatment period.

An Interactive Response System (IRS) will provide study treatment group assignments (using a computer-generated randomization code provided by the IRS vendor) and dosing adjustments. An independent, unblinded Data Safety Monitoring Board (DSMB) will be established to oversee the IRS and verify the appropriateness of all dosing adjustments, and to monitor subject safety and the effectiveness of CTAP101 Capsules at regular intervals. Members of the DSMB will also conduct periodic reviews of study conduct to verify that all

required data are captured to a sufficiently high degree (>95%) and within specified time frames (usually within 5 days), and to promptly recommend appropriate corrective actions to address any noted deficiencies, in an effort to minimize missing data. Specific responsibilities and activities of the DSMB will be defined in the charter ratified at the pre-study organizational meeting. These responsibilities will include the completion of an interim analysis of the data obtained from Cohort 1 to justify a starting dose for Cohort 2, and an interim analysis of the data obtained from Cohort 2 to justify a starting dose for a separate phase 2 study in subjects having ages of 1 month to <8 years.

Subjects receiving treatment prior to study enrollment with calcitriol or another 1 α -hydroxylated vitamin D analog, or calcimimetics prior to study enrollment will forgo further dosing with these agents for the duration of the study and complete an 8-week washout period prior to baseline assessments.

[figure not shown]
Subjects receiving vitamin D supplementation at a rate above 1,700 IU/day or 50,000 IU (1,250 mcg) per month prior to study enrollment must reduce the dose to \leq 1,700 IU/day for the duration of the study and undergo an 8-week washout period prior to baseline assessments if serum total 25-hydroxyvitamin D is \geq 30 ng/mL. The washout period is unnecessary if serum total 25-hydroxyvitamin D is <30 ng/mL. Subjects will complete a 6-week follow-up (FU) period after completing the 26-week treatment period or after early termination (ET).

Blood samples will be collected at weekly, biweekly or monthly intervals during the 10-week pre-treatment screening/baseline period, the 26-week treatment period and the 6-week post-treatment FU period. Sparse PK samples will be collected from all subjects on Day 83 at 0 (pre-dose), 6, 12, 24 hours (Day 84 pre-dose) and 48 hours (Day 85 pre-dose). Additional PK blood samples will be collected in both Cohort 1 and Cohort 2 in subsets of 10 subjects treated with CTAP101 Capsules and 5 subjects treated with placebo during the last 3 days of the 12th week of treatment (prior to dose titration). The additional PK samples will be collected as follows: Day 83: -2, 2, 4 and 8 hours. End of study PK blood samples will be collected in other subsets of approximately 20 subjects (20 subjects from each cohort) during the post-treatment FU period. In each cohort, an attempt will be made to collect PK samples from 10 subjects on each ending daily dose level (30 or 60 mcg) of CTAP101 Capsules, in order to establish the terminal elimination half-lives ($t_{1/2}$) of 25-hydroxyvitamin D₃ at each of these dose levels.

[figure not shown]
All subjects, study personnel and the sponsor will be blinded to the administered treatments and to plasma iPTH, serum total 25-hydroxyvitamin D and serum 25-hydroxyvitamin D₃ data until the last subject completes 26 weeks of treatment. Unblinded data will be provided to all study sites when the final clinical study report becomes available.

An interim analysis of data obtained from the 15 subjects in Cohort 1 who provide intensive PK samples during the last three days of treatment week 12 will be undertaken by the DSMB to determine the appropriate starting dose for Cohort 2. A second interim analysis of data obtained from 15 subjects in Cohort 2 who provide intensive PK samples during the last three days of treatment week 12 will be undertaken by the DSMB to determine the appropriate starting dose for a separate phase 2 study in subjects of ages 1 month to <8 years.

A diagram of the study design for Cohort 1 (n=~72) is shown below:

A diagram of the study design for Cohort 2 (n=~36) is shown below:

Duration of Study:

Each subject will participate in the study for up to approximately 42 weeks (2-weeks screening/baseline, 8-weeks washout, if required, 26-weeks of treatment with CTAP101 Capsules or matching placebo, and 6-weeks of FU evaluation).

Study Parameters:

Key parameters to be monitored at regular intervals during the study include: plasma iPTH, serum calcium (corrected for serum albumin), serum phosphorus, serum CaxP product, serum total 25-hydroxyvitamin D, serum 25-hydroxyvitamin D₃, and urine calcium:creatinine ratio. Vital signs (VS) and adverse events (AEs) will be monitored at each study visit. Other parameters to be monitored less frequently include brief physical examinations (PEs), clinical laboratory tests (hematology and clinical and urine chemistries) and patient-reported palatability and acceptability. Twelve-lead electrocardiograms (ECGs) will be obtained at baseline and at the end of treatment or ET. [REDACTED]

[REDACTED]

[REDACTED]

Dosing Plan:

Subjects in Cohort 1 will receive two capsules (CTAP101 Capsules and/or matching placebo capsules) every day at bedtime to achieve the targeted initial daily dose of 30 mcg of calcifediol (one CTAP101 capsule plus one placebo capsule) or 0 mcg of calcifediol (two placebo capsules). Any food intake within 60 minutes of medication administration will also be recorded. At the end of 12 weeks of treatment, subjects assigned to active treatment will undergo upward dose titration to 60 mcg per day (two CTAP101 Capsules) provided that (a) plasma iPTH has not decreased by at least 30% from pretreatment baseline, (b) corrected serum calcium is <9.8 mg/dL, (c) serum phosphorus is ≤5.5 mg/dL and (d) serum total 25-hydroxyvitamin D is ≤65 ng/mL. Subjects in Cohort 2 will receive a starting daily bedtime dose which will be determined on the basis of the interim analysis of data obtained in Cohort 1 (see above), and will undergo upward dose titration to a new daily dose that is two times higher than the starting dose at the end of 12 weeks of treatment, provided that (a) plasma iPTH has not decreased by at least 30% from pretreatment baseline, (b) corrected serum calcium is <9.8 mg/dL, (c) serum phosphorus is >6.0 mg/dL and (d) serum total 25-hydroxyvitamin D is ≤65 ng/mL.

Subjects in both cohorts will reduce the dose by one capsule per week, as necessary, and no more frequently than at biweekly intervals, in the event that any one of the following four criteria are met: plasma iPTH is confirmed to be <35 pg/mL (for subjects with stage 3 CKD) or <70 pg/mL (for subjects with stage 4 CKD), serum calcium (corrected) is confirmed to be >10.3 mg/dL, serum total 25-hydroxyvitamin D is confirmed to be >100 ng/mL, or serum phosphorus is confirmed to be >5.5 mg/dL (ages 12 to <18 years) or >6.0 mg/dL (ages 8 to <12 years), provided that the investigator has deemed the elevated serum phosphorus to be related to study drug administration and has taken appropriate and persistent actions to control serum phosphorus by initiating or adjusting any phosphate binder therapy.

Dose reductions will be accomplished by consistently omitting doses on a specific day of the week, as follows:

- First dose reduction: Dosing will be omitted on all Mondays (M).
- Second dose reduction: Dosing will be omitted on all M and Wednesdays (W)
- Third dose reduction: Dosing will be omitted on all M, W and Fridays (F)
- Fourth dose reduction: Dosing will be omitted on all M, W, F and Sundays (S)

Any subject who requires a further dose reduction will terminate dosing with study drugs and immediately commence the 6-week FU period.

Subjects on dose reduction will be allowed an unscheduled safety visit if deemed appropriate by the investigator to have FU blood sampling within 48 hours of any dose reduction.

A summary of the initial and reduced weekly dose levels, in mcg units, after each of the four possible dose reductions appears in the table below:

Daily (mcg)	Weekly (mcg)	Weekly Dose (mcg)			
		1 st Reduction	2 nd Reduction	3 rd Reduction	4 th Reduction
60	420	360	300	240	180
30	210	180	150	120	90
0	0	0	0	0	0

Subjects will suspend dosing if plasma iPTH is persistently <30 pg/mL (three consecutive visits) or serum calcium (corrected) is confirmed to be >11.0 mg/dL, and resume when iPTH is ≥ 35 pg/mL and serum calcium is <9.8 mg/dL at the next lower dose level.

Primary Efficacy Endpoint:

The primary estimand is the reduction of mean plasma iPTH by at least 30% from pre-treatment baseline. The primary efficacy endpoint is the proportion of subjects in the intent-to-treat (ITT) population (age 8 to <18 years) attaining a mean decrease in plasma iPTH of at least 30% from pre-treatment baseline compared to placebo during the EAP.

Primary Safety Endpoints:

Safety and tolerability will be evaluated in the safety population by AEs, PEs, VS, hematology and clinical chemistries, and ECGs.

Pharmacokinetic Endpoints:

For the interim analysis, repeated-dose (steady-state) PK determinations will be performed in subsets of subjects in both Cohort 1 and Cohort 2 by analyzing serum 25-hydroxyvitamin D₃ concentrations versus time recorded during dosing with CTAP101 Capsules (n=10) or placebo (n=5) in the last three days of the 12th week of treatment.

For the final analysis, repeated-dose (steady-state) PK determinations will be performed in both Cohort 1 and Cohort 2 by analyzing serum 25-hydroxyvitamin D₃ concentrations versus time recorded (a) during dosing with CTAP101 Capsules or placebo in the last three days of the 12th week of treatment and (b) after the last administered dose in each active treatment group.

The following PK parameters will be calculated using observed and baseline-adjusted 25-hydroxyvitamin D₃ concentrations: (a) area under the concentration curve (AUC), maximum concentration, (C_{\max}), time to maximum concentration (t_{\max}), and steady-state concentration (C_{ss}); and (b) $t_{1/2}$, clearance (CL/F) and volume of distribution (Vd/F), as feasible. Relative exposure and dose proportionality will be examined, if possible.

Secondary Endpoints:

Secondary efficacy endpoints include the proportion of subjects in the per-protocol (PP) population attaining a mean decrease in plasma iPTH of at least 30% from pre-treatment baseline during the EAP and the proportions of subjects in the ITT and PP populations attaining a mean serum total 25-hydroxyvitamin D of at least 30 ng/mL, in aggregate and by mean weekly study dose in the EAP. Additional secondary endpoints include the time courses of mean absolute changes from pre-treatment baseline in serum total 25-hydroxyvitamin D and plasma iPTH; PD effects on mean serum calcium (corrected), serum phosphorus, serum CaxP product, and the urine calcium:creatinine ratio; the proportion of subjects in each treatment group with hypercalciuria (>200 mg calcium/g creatinine), hypercalcemia (2 consecutive visits with serum calcium >10.3 mg/dL) or hyperphosphatemia (2 consecutive visits with serum phosphorus >5.5 mg/dL (ages 12 to <18 years) or >6.0 mg/dL (ages 8 to <12 years), deemed to be study drug related); and the proportion of subjects who attain 2 consecutive plasma iPTH values ≤ 70 pg/mL.

[REDACTED]

[REDACTED]

[REDACTED]

Additional Assessments:

Patient reported outcomes on palatability and acceptability.

Sample Size Estimation:

Sample size has been calculated (using Fisher's exact test statistics) to provide power of 80% for a two-sided, alpha 0.05 level test of equal proportions comparing the percentages of subjects attaining mean decreases of at least 30% in plasma iPTH (averaged over the last 6 weeks of treatment) compared to baseline on daily dosages of CTAP101 Capsules versus placebo. Assuming response rates of at least 0.4 (CTAP101 Capsules) versus 0.1 (placebo), and using a 2:1 ratio of CTAP101 Capsules:placebo subjects with an estimated 20% dropout rate over the course of the study, a sample size of approximately 108 subjects is required in the study with two-thirds apportioned to the 12 to <18 year age group (Cohort 1) and one-third apportioned to the 8 to <12 year age group (Cohort 2), allocated as 72 subjects to CTAP101 Capsules and 36 subjects to placebo.

Statistical Analyses:

Efficacy analyses will be performed for the ITT and PP populations, as indicated. The ITT population will be defined as all subjects who have been randomized to receive study medication. The PP population will be defined as all subjects for whom at least two plasma

iPTH determinations are included in the calculated baseline value, defined as weeks -2 through -1, and in the EAP, and who do not have a major protocol deviation.

Primary efficacy will be assessed in the ITT population by comparing the proportions of subjects in each treatment group (CTAP101 Capsules versus placebo) attaining a mean decrease from baseline in plasma iPTH of $\geq 30\%$ in the EAP using the Cochran-Mantel-Haenszel test statistic (alpha=0.05) for overall efficacy of the multicenter results. Subjects who do not have at least two plasma iPTH determinations in the EAP will be deemed non-responders.

Secondary efficacy will be assessed in the PP population by comparing the proportions of subjects in each active treatment group attaining mean decreases in plasma iPTH of $\geq 30\%$ (from baseline) in the EAP to the corresponding proportion of subjects in the placebo group, and in the ITT and PP populations by comparing the proportions of subjects in each active treatment group attaining mean serum total 25-hydroxyvitamin D of ≥ 30 ng/mL in the EAP to the corresponding proportions of subjects in the placebo group, in aggregate and by mean weekly study dose in the EAP. Mean weekly dose in the EAP will be calculated for three groups of subjects: those receiving 0 mcg per day; those receiving >0 and ≤ 30 mcg per day; and, those receiving >30 mcg/day of calcifediol.

Primary safety analyses will be conducted in the ITT population, and the statistical summary will be descriptive and performed by treatment group. No inferential hypothesis testing will be performed on the safety parameters with the exception of serum calcium, serum phosphorus, serum CaxP product, and urine calcium:creatinine ratio.

Secondary safety analyses will compare the proportions of subjects with confirmed corrected serum calcium >10.3 mg/dL or confirmed serum phosphorus >5.5 mg/dL (ages 12 to <18 years) or >6.0 mg/dL (ages 8 to <12 years) (deemed to be study drug related) or serum confirmed CaxP product >55 (for Cohort 1) or >60 (for Cohort 2) between the CTAP101 Capsules and placebo treatment groups using the Cochran-Mantel-Haenszel test statistic (alpha=0.05) for overall safety in the multicenter results.

Descriptive statistics will be applied to evaluate patient reported palatability and acceptability.

Inclusion Criteria:

Each subject must meet the following criteria to be enrolled in this study:

1. Cohort 1: Be 12 to <18 years of age and have a body weight of ≥ 40 kg; Cohort 2: be 8 to <12 years of age and have a body weight of ≥ 20 kg.
2. Be diagnosed with stage 3 or 4 CKD at least six months prior to the screening visit, and have an estimated glomerular filtration rate (eGFR) of ≥ 15 to <60 mL/min/1.73m² at screening.
3. Be without any disease state or physical condition that might impair evaluation of safety or which, in the investigator's opinion, would interfere with study participation, including:
 - a. Serum albumin ≤ 3.0 g/dL;
 - b. Serum transaminase (alanine transaminase [ALT], glutamic pyruvic transaminase [SGPT], aspartate aminotransferase [AST] or glutamic oxaloacetic transaminase [SGOT]) > 2.5 times the upper limit of normal at screening, and,

- c. Urinary albumin excretion of >3000 mcg/mg creatinine.
4. Exhibit during the initial or, if necessary, a screening visit after washout:
 - a. Plasma iPTH >100 pg/mL (stage 3 CKD) or >160 pg/mL (stage 4 CKD)
 - b. Serum calcium <9.8 mg/dL (corrected for albumin);
 - c. Serum total 25-hydroxyvitamin D <30 ng/mL; and,
 - d. Serum phosphorus >2.5 to ≤ 5.5 mg/dL (12 to <18 years) or ≤ 6.0 mg/dL (ages 8 to <12 years).
5. If taking calcitriol or other 1α -hydroxylated vitamin D analogs, or cinacalcet, be willing to forgo treatment with these agents for the duration of the study and complete an 8-week washout period prior to commencing treatment in the study.
6. If taking more than 1,000 mg/day of elemental calcium, discontinue or reduce calcium use and/or use non-calcium based therapies for the duration of the study.
7. If receiving $\leq 1,700$ IU/day nutritional vitamin D (ergocalciferol or cholecalciferol) therapy, must agree to remain on a stable dose during the study.
8. If taking more than 1,700 IU/day of nutritional vitamin D, must discontinue or decrease the dose to $\leq 1,700$ IU/day, maintain that dose for the duration of the study, and complete an 8-week washout period prior to commencing treatment in the study provided that serum total 25-hydroxyvitamin D is ≥ 30 ng/mL. The washout period is not necessary if serum total 25-hydroxyvitamin D is <30 ng/mL.
9. If taking any bone metabolism therapy that could interfere with study endpoints, must discontinue use of such agent(s) for the duration of the study.
10. Willing and able to comply with study instructions and commit to all clinic visits for the duration of the study.
11. Female subjects of childbearing potential must be neither pregnant nor lactating and must have a negative urine pregnancy test at the first screening visit.
12. All female subjects of childbearing potential and male subjects with female partners of childbearing potential must agree to use effective contraception (eg, implants, injectables, combined oral contraceptives, intrauterine device, sexual abstinence, vasectomy or vasectomized partner) for the duration of the study.
13. Each subject or their legal representative must be able to read, understand and sign the Informed Consent Form (ICF).

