4.2 Inclusion Criteria

Each subject must meet the following criteria to be enrolled in this study:

1. Cohort 1: Be 12 to <18 years of age and have a body weight of ≥ 40 kg; Cohort 2: be 8 to <12 years of age and have a body weight of ≥ 20 kg.
2. Be diagnosed with stage 3 to 4 CKD at least six months prior to the screening visit, and have an eGFR of ≥ 15 to <60 mL/min/1.73m² at screening.
3. Be without any disease state or physical condition that might impair evaluation of safety or which, in the investigator's opinion, would interfere with study participation, including:
 - a. Serum albumin ≤ 3.0 g/dL;
 - b. Serum transaminase (ALT or SGPT, AST or SGOT) > 2.5 times the upper limit of normal at screening; and,
 - c. Urinary albumin excretion of >3000 mcg/mg creatinine.
4. Exhibit during the initial or, if necessary, a screening visit after washout:
 - a. Plasma iPTH >100 pg/mL (stage 3 CKD) or >160 pg/mL (stage 4 CKD)
 - b. Serum calcium <9.8 mg/dL (corrected for albumin);
 - c. Serum total 25-hydroxyvitamin D <30 ng/mL; and,
 - d. Serum phosphorus >2.5 to ≤ 5.5 mg/dL (12 to <18 years) or ≤ 6.0 mg/dL (ages 8 to <12 years);
5. If taking calcitriol or other 1 α -hydroxylated vitamin D analogs, or cinacalcet, be willing to forgo treatment with these agents for the duration of the study and complete an 8-week washout period prior to commencing treatment in the study.
6. If taking $>1,000$ mg/day of elemental calcium, discontinue or reduce calcium use and/or use non-calcium based therapies for the duration of the study.
7. If receiving $\leq 1,700$ IU/day nutritional vitamin D (ergocalciferol or cholecalciferol) therapy, must agree to remain on a stable dose during the study.
8. If taking $>1,700$ IU/day of nutritional vitamin D, must discontinue or decrease the dose to $\leq 1,700$ IU/day, maintain that dose for the duration of the study, and complete an 8-week washout period prior to commencing treatment in the study provided that serum total 25-hydroxyvitamin D is ≥ 30 ng/mL. The washout period is not necessary if serum total 25-hydroxyvitamin D is <30 ng/mL.
9. If taking any bone modifying treatment that could interfere with study endpoints, must discontinue use of such agent(s) for the duration of the study.

10. Willing and able to comply with study instructions and commit to all clinic visits for the duration of the study.

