5.3 Selection and Timing of Dose for Each Subject

Subjects in Cohort 1 will receive two capsules (CTAP101 Capsules and/or matching placebo capsules) every day at bedtime to achieve the targeted initial daily dose of 30 mcg of calcifediol (one CTAP101 Capsule plus one placebo capsule) or 0 mcg of calcifediol (two placebo capsules). Any food intake within 60 minutes of medication administration will also be recorded. At the end of 12 weeks of treatment, subjects assigned to active treatment will undergo upward dose titration to 60 mcg per day (two CTAP101 Capsules) provided that (a) plasma iPTH has not decreased by at least 30% from pretreatment baseline, (b) corrected serum calcium is <9.8 mg/dL, (c) serum phosphorus is \leq 5.5 mg/dL, and (d) serum total 25-hydroxyvitamin D is \leq 65 ng/mL. Subjects in Cohort 2 will receive a starting daily bedtime dose which will be determined on the basis of the interim analysis of data obtained in Cohort 1, and will undergo upward dose titration at the end of 12 weeks of treatment to a new daily dose that is two times higher than the starting dose, provided that (a) plasma iPTH has not decreased by at least 30% from pretreatment baseline, (b) corrected serum calcium is <9.8 mg/dL, (c) serum phosphorus is \leq 6.0 mg/dL and (d) serum total 25-hydroxyvitamin D is \leq 65 ng/mL.

In order to maintain blinding, subjects will receive periodic supplies of study drug in bottles of identical appearance, some labeled “Bottle 1” and some labeled “Bottle 2,” along with the same dosing instructions regardless of randomization group directing the subject to take one capsule from one bottle labeled “Bottle 1” and one bottle labeled “Bottle 2” every day at bedtime.

An unblinded medical monitor who will be part of the independent, unblinded DSMB will oversee study drug assignments and dose adjustments (see below) by IRS.

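### The Synopsis reverses the phosphorus criterion for doubling the dose in children aged 8 to <12 years, and its restart rule is looser on iPTH than Section 5.4 for stage 4 CKD

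*Combined protocol and SAP*

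**What the plan says.** **Up-titration at week 12, Cohort 2.** The Synopsis (Dosing Plan) and Section 5.3 each list four conditions (a) to (d) for doubling the starting dose. They agree on (a) iPTH not yet down by 30%, (b) corrected calcium <9.8 mg/dL and (d) total 25-hydroxyvitamin D ≤65 ng/mL. They differ on (c):

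- Synopsis: "c) serum phosphorus is >6.0 mg/dL and (d".
- Section 5.3: "c) serum phosphorus is \leq 6.0 mg/dL" (the symbol is less-than-or-equal).

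**Related phosphorus rules.**

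- Cohort 1 titration, in the same Synopsis paragraph: "c) serum phosphorus is ≤5.5 mg/dL and (d) serum total".
- Entry, Section 4.2, criterion 4d: "mg/dL (12 to <18 years) or ≤ 6.0 mg/dL (ages 8 to <12 years".
- Dose-reduction trigger, Synopsis, with Section 5.4 to the same effect: ">6.0 mg/dL (ages 8 to <12 years), provided that the investigator has deemed the elevated serum phosphorus to be related".
- Hyperphosphatemia, Synopsis (Secondary Endpoints), needing two consecutive visits: ">6.0 mg/dL (ages 8 to <12 years), deemed to be study drug related".

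**Restart after suspension.** The Synopsis lets any subject resume once iPTH is at least 35 pg/mL "and serum calcium is <9.8 mg/dL at the next lower dose level". Section 5.4 keeps 35 pg/mL for stage 3 CKD but requires at least 70 pg/mL for stage 4, with calcium ≤9.8 mg/dL.

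**The concern.** Criterion (c) is there to keep the dose from being raised in a child whose phosphorus is already too high. As the Synopsis words it, high phosphorus becomes a condition for doubling, and a child within the limit is refused.

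The stake is a dosing decision in 8 to <12 year olds. Section 1.13 reports a larger phosphorus rise on active drug than on placebo in adults (0.2 versus 0.1 mg/dL). Section 5.5 states that there is no specific antidote and that the half-life is about 30 days in adults with CKD. The dose-reduction rule would not promptly undo a wrong increase: it needs two consecutive high values, a judgement that they are drug related, and action on phosphate binders.

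Dose changes are made through the IRS, which has to be programmed from some text. The documents do not say whether the Synopsis or the body prevails. The IRS specification and the DSMB charter are not among them, so it is unknown which version would be applied.

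**Working it through.** The protocol gives no figure to reproduce here. The check is a comparison of texts, followed by simple arithmetic on its reach.

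**1. Decisions at week 12 in Cohort 2 when (a), (b) and (d) are met**

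| Phosphorus | Synopsis | Section 5.3 |
|---|---|---|
| ≤6.0 mg/dL | do not double | double |
| >6.0 mg/dL | double | do not double |

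The two conditions are exact complements, so no value satisfies both. If (a), (b) or (d) fails, both texts refuse titration and there is no conflict.

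**2. Which text is wrong**

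The four related rules all treat phosphorus above the age limit as unacceptable: for titration in Cohort 1, for entry, for continuing at the same dose once confirmed and drug related, and as a safety outcome. Only the Synopsis criterion for Cohort 2 points the other way. A fault in reading the PDF is unlikely, because the ≤ signs for 5.5 mg/dL and 65 ng/mL in the same paragraph came through correctly.

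**3. How many subjects**

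- Cohort 2 is about 36 subjects randomized 2:1 (Section 3.1), so active = 36 × 2/3 = 24.
- Planned dropout is 20% over the study (Section 9.2). If all of it fell before week 12, 24 × 0.8 = 19.2.
- Only those meeting (a), (b) and (d) are affected. The documents give no paediatric rates, so a range is assumed:

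| Assumed share meeting (a), (b), (d) | Of 19.2 | Of 24 |
|---|---|---|
| 25% | 4.8 | 6 |
| 50% | 9.6 | 12 |
| 75% | 14.4 | 18 |

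These are opposite decisions of both kinds: wrongly doubled (phosphorus >6.0) and wrongly refused (phosphorus ≤6.0). The split cannot be derived from the documents.

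**4. Consistency with the calcium-phosphorus product**

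The secondary safety analysis in the Synopsis uses "CaxP product >55 (for Cohort 1) or >60 (for Cohort 2" as its thresholds.

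- Cohort 1 titration limits: product below 9.8 × 5.5 = 53.9, under 55.
- Cohort 2 limits in Section 5.3: product below 9.8 × 6.0 = 58.8, under 60.
- Cohort 2 rule in the Synopsis: phosphorus has no upper limit. Calcium 9.0 with phosphorus 6.7 gives 9.0 × 6.7 = 60.3, and the dose would still be doubled.

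The Section 5.3 limits fit the analysis thresholds in the same way in both cohorts; the Synopsis rule does not.

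**5. Restart rule**

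A suspended stage 4 subject with iPTH of 35 to <70 pg/mL and calcium <9.8 mg/dL may resume under the Synopsis but not under Section 5.4. That iPTH range also lies inside the stage 4 dose-reduction trigger (<70 pg/mL at two consecutive visits, Section 5.4). The calcium limits (<9.8 versus ≤9.8) differ only at exactly 9.8 mg/dL, and there the Synopsis is the stricter text.

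**The case against.** The strongest reply is that this is an evident slip of one symbol. The dedicated dosing section is right, and every neighbouring rule shows what was meant. Sites cannot apply the Synopsis rule themselves, because they are blinded to treatment, iPTH and 25-hydroxyvitamin D (Section 5.7). An unblinded DSMB, with an unblinded medical monitor, checks the dose changes (Sections 5.3, 5.7 and 10.8), and Cohort 2 opens only after FDA approval (Section 3.1). All of this stands and lowers the chance of harm. It does not correct the rule, and the people who check still need one rule to check against.

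Three points on size also stand:

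- Entry requires phosphorus ≤6.0 mg/dL. If most children stay near their entry range, most of the opposite decisions would be wrongly refused increases, so the counts above are not counts of children put at risk by a doubled dose. Refusal would fall on children who have not reached the 30% iPTH reduction. It could bear on response in the efficacy assessment period, but no size can be given.
- The product threshold of 60 belongs to the safety analysis. No dosing rule uses it, and a single value of 60.3 would not count as confirmed.
- Restart is at the next lower dose in both texts, which makes the restart mismatch minor.

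**Conclusion.** The concern holds. The Cohort 2 phosphorus criterion in the Synopsis is reversed and, if followed, gives the wrong decision for every subject who meets the other three criteria. At most about 24 active subjects are concerned, or about 19 if all planned dropout came before week 12. The range of 5–6 to 14–18 opposite decisions rests on the assumed shares of 25% to 75%.

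The restart mismatch is real but secondary. It affects only suspended stage 4 subjects with iPTH of 35 to <70 pg/mL.

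No child is shown to have been misdosed, and no effect on the primary endpoint is claimed. Practical harm depends on which text was programmed. It still needs correcting, because it is a dose-escalation safety rule in children and not background wording.

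**What to change.** - In the Synopsis (Dosing Plan), change Cohort 2 criterion (c) to phosphorus ≤6.0 mg/dL, as in Section 5.3.
- In the Synopsis restart rule, require iPTH ≥35 pg/mL for stage 3 and ≥70 pg/mL for stage 4, as in Section 5.4.
- Use one calcium restart limit in both places. A limit of <9.8 mg/dL matches the entry and titration criteria.
- Check the IRS specification and the DSMB charter against the corrected rules before Cohort 2 opens.

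The cost is a short clarifying amendment and a document check, with no added patients, visits or analyses.
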